7.9.2.3. Analysis Methods and Presentation Format

The mean and standard deviation of the pain scores (including overall, back, and leg pain) will be summarized at each follow-up visit. The change in pain scores will be summarized too. As an additional analysis, if a subject drops out of the study due to dissatisfaction with the therapy, the subject's pain scores at dropout will be used at the subsequent lower percentages of amplitude where data was not collected

The percentage of amplitude from perception threshold for maintaining overall pain relief will be summarized. In case subjects drop out during follow-up, the percentage of amplitude prior to subject dropout will be used as the minimum amplitude in the summary.

In addition, a repeated measure analysis may be applied to examine the relationship between the change in pain score and percent amplitude. The dependent variable will be the change in pain score,

the independent variables will be percent amplitude and visit as fixed effects, and subject as the random effect. The interaction term of percent amplitude by visit will be tested and kept out of the model if it is not significant.

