9.4.2. Baseline/Programming Visit #1

The Baseline/Programming Visit #1 will be targeted to take place at least 2 weeks after the Screening visit. At the beginning of the Baseline visit, subjects will return their completed diary, complete the Subject Satisfaction Assessment (SSA), and baseline eligibility criteria will be assessed.

To proceed on with the Baseline visit, the subject must meet the following inclusion criteria:

- 1. Has an average overall VAS pain score ≤ 4 based on the Baseline diary

To proceed on with the Baseline visit, the subject must not meet any of the following exclusion criteria:

- 1. Has provided response to Baseline SSA as “Neutral”, “Somewhat unsatisfied”, or “Very unsatisfied” with the therapy
- 2. Completed less than 5 of the 7 days of the Baseline diary

Subjects who do not meet Baseline eligibility criteria will be exited from the study and will be considered a screen failure.

[Redacted]

On the day of the Baseline visit, or during the course of the study, subjects must have imaging performed (eg, fluoroscopy or x-ray), which will be annotated with a vertebral marker.

Each subject’s device will be interrogated and a report session will be generated to capture the subject’s initial active therapy settings.

The perception threshold and description of the sensation will be collected for Setting 1 (90 μ s and 1000 Hz) with subjects in both the supine and sitting positions. [Redacted]

[Redacted]

Table 3: Perception Threshold Settings

	Pulse Width	Frequency
Setting 1	90 μ s	1000 Hz
[Redacted]	[Redacted]	[Redacted]
[Redacted]	[Redacted]	[Redacted]
[Redacted]	[Redacted]	[Redacted]

[Redacted]

Each subject's device will be programmed with four groups at 90 μ s and 1000 Hz. The active anode and cathode in each group will remain the same as what the subject used during the Baseline period and should remain the same for the duration of the study. The only difference between the four groups will be the amplitude, which will be set to 80%, 60%, 40%, and 20% of the determined amplitude perception thresholds in the sitting and supine positions with AdaptiveStim™ enabled. If subjects are unable to reach a perception threshold at 90 μ s and 1000 Hz, the maximum amplitude allowed by the device (9.9 volts) will be used as the perception threshold.

Subjects will begin their first treatment period programmed to the group with 80% perception threshold and AdaptiveStim™ enabled.

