9.4.3. Programming Visits #2, #3, and #4

Beginning approximately two weeks after the Baseline visit, in accordance with the targeted windows in Section 9.4.6, subjects will return to the clinic for Programming Visit #2 and should bring back their completed diary. After Programming Visit #2, subjects will return to the clinic about every two weeks for Programming Visits #3 and #4.

During Programming Visits #2, #3, and #4, subjects will be asked to complete the SSA to reflect their satisfaction of the last therapy setting. Subjects will also record on the SSA whether they have felt any stimulation sensations during the last follow-up period and, if so, to describe the sensation.

Each subject's device will be interrogated and a report session will be generated to capture the subject's initial active therapy settings.

With the device programmed to 90 μ s and 1000 Hz, the amplitude will be programmed based on the perception thresholds obtained in the supine and sitting positions during the Baseline visit as follows:

- Programming Visit #2: 60% of Baseline perception threshold
- Programming Visit #3: 40% of Baseline perception threshold
- Programming Visit #4: 20% of Baseline perception threshold

If subjects are unable to reach a perception threshold at 90 μ s and 1000 Hz, the maximum amplitude allowed by the device (9.9 volts) will be used as the perception threshold.

At the conclusion of programming, a report session will be generated to capture the subject's final active therapy settings.

Subjects will be provided a diary to record their VAS pain scores for the last week of each follow-up period. Subjects should bring back their completed diary each time they return to the clinic at the end of a follow-up period. A telephone call will be placed to the subjects one week before they return to the clinic to remind them to begin completing the diary.

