9.10. Subject Withdrawal or Discontinuation

A subject has the right to withdraw from the study at any time and for any reason without prejudice to their future medical care by the principal investigator or institution. Subjects will be provided standard medical care by their physician after their study participation ends.

The study sample size accounts for expected attrition, thus exited subjects will not be replaced.

Examples of reasons for study exit include the following:

- Subject death
- Subject lost to follow-up
- Subject voluntarily withdraws from the study
- Subject becomes pregnant
- Investigator terminates the subject's participation in the study due to lack of compliance, violation of/change in eligibility criteria
- Any clinical laboratory abnormality, inter-current illness, or other medical condition or situation occurs such that continued study participation would not be in the best interest of the subject
- Normal study completion

A study exit eCRF will be completed for all enrolled subjects; the reason for withdrawal shall be recorded on the study exit eCRF. If a subject exits from the study prior to normal completion, the eCRFs for visits that have occurred up to the point of withdrawal as well as the study exit eCRF should be completed. If a subject exits due to an adverse event or device deficiency, the appropriate event eCRFs should also be completed.

If the subject proceeds beyond the Baseline/Programming Visit #1 but chooses to withdraw from the study early; if they are willing, the Final Study Visit procedures may be completed prior to study exit.

If a subject requires a system modification or replacement during the study, they should be exited from the study.

In the case that the subject is determined to be lost to follow-up, details of a minimum of two attempts and the method of attempt (e.g., one letter and one phone record or two letters) to contact the subject must be recorded in the subject's medical records. In addition, regulations set forth by the governing IRB must be followed.

10. Risks and Benefits

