7.4. Handling of Missing, Unused, and Spurious Data and Dropouts

Missing data are a potential source of bias when analyzing study data. A rigorous study design and execution will help prevent the incidence of missing data from occurring.

The analysis of the primary and secondary objectives will use subjects who provide data. The purpose of the study is to characterize the minimum amplitude that maintains SCS therapy satisfaction and overall pain relief; in case subjects drop out during follow-up, the percentage of amplitude prior to dropout will be used to summarize the minimum amplitude.

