7.7. Treatment Characteristics

Subjects are implanted before enrolling into the study, so the surgical procedures are not described in the study. The neurostimulator and lead(s) model will be summarized. Subjects proceed beyond baseline visit will receive 4 different programmed amplitude setting in the following order: 80%, 60%, 40%, and 20% of perception threshold amplitude, each for approximately two weeks. Subject assessments are collected at each following up visit.

Subjects' pain medications will be collected. All pain medications will be coded using the appropriate version of the World Health Organization (WHO) Drug Dictionary at the appropriate Anatomical Therapeutic Chemical (ATC) level.

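### On the planned schedule, percent amplitude and visit are aliased in the optional repeated-measures model, so neither a visit-adjusted amplitude effect nor the interaction test in SAP 7.9.2.3 can be obtained as described

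*SAP*

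**What the plan says.** SAP 7.9.2.3 adds an optional model to the descriptive summaries of the secondary objective: "In addition, a repeated measure analysis may be applied to examine the relationship between the change in pain score and percent amplitude". The outcome is change in pain score, and "the independent variables will be percent amplitude and visit as fixed effects, and subject as the random effect". An interaction rule follows: "The interaction term of percent amplitude by visit will be tested and kept out of the model if it is not significant". The SAP does not say whether either term is a factor or a linear covariate.

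The schedule is fixed. SAP 7.7 states: "Subjects proceed beyond baseline visit will receive 4 different programmed amplitude setting in the following order: 80%, 60%, 40%, and 20"% of perception threshold. Protocol 9.4.2 gives the first step, "Subjects will begin their first treatment period programmed to the group with 80% perception threshold", and Protocol 9.4.3 continues with "Programming Visit #2: 60% of Baseline perception threshold", then 40% at Visit #3 and 20% at Visit #4. The visible text describes no randomised order, repeated setting or parallel group.

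Two further passages matter for early leavers. Protocol 9.10 says that, for a willing subject who withdraws after Baseline, "the Final Study Visit procedures may be completed prior to study exit". SAP 7.4 says "The analysis of the primary and secondary objectives will use subjects who provide data".

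**The concern.** If each follow-up visit carries exactly one amplitude, the data cannot say whether a rise in pain came from the lower setting or from the passage of time. A model with both terms then has more parameters than the design can support. Software will usually still produce output by setting some parameters to zero, so what is reported as the amplitude effect may depend on the coding or on which term is dropped. If visit is dropped, a combined effect of amplitude, time and order could be reported as if it were adjusted for visit. The interaction rule has the same problem: it decides the final model through a test that either does not exist or tests something else.

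This is the only model in the visible text that relates pain change to amplitude, which is the purpose of the study.

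**Working it through.** The documents give no numerical result for this model, so there is no stated figure to reproduce. The check is of identifiability.

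**Inputs**
- Order 80, 60, 40, 20%, one assessment per setting: SAP 7.7, Protocol 9.4.2 and 9.4.3.
- 40 treated subjects: SAP section 6. This number does not affect the aliasing.
- Model terms: SAP 7.9.2.3.
- Assumption: percent amplitude means the programmed percentage of the Baseline threshold, and visit is the follow-up number 1 to 4.

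**Step 1: the relation between the terms.** Amplitude = 100 − 20 × visit, with correlation −1.

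**Step 2: rank of the fixed-effect design**, 40 complete subjects × 4 records = 160 rows.

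| Coding | Columns / rank, main effects | Amplitude df given visit | Columns / rank with interaction | Interaction df |
|---|---|---|---|---|
| Both factors | 7 / 4 | 0 | 16 / 4 | 0 |
| Amplitude factor, visit linear | 5 / 4 | 2 | 8 / 4 | 0 |
| Amplitude linear, visit factor | 5 / 4 | 0 | 8 / 4 | 0 |
| Both linear | 3 / 2 | 0 | 4 / 3 | 1 |

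The 2 df in the second row test departure from a straight line only, because the linear trend is shared with visit.

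**Step 3: the one interaction that can be computed.** With both terms linear, visit = (100 − amplitude)/20, so amplitude × visit = 5 × amplitude − amplitude²/20. At 80, 60, 40 and 20% this gives 80, 120, 120 and 80. The test is of curvature in amplitude, not of an amplitude effect that changes over visits.

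**Step 4: two different truths, same data.** A pure amplitude effect of 0.5 point per step down and a pure time effect of 0.5 point per period both give mean changes of 0, 0.5, 1.0 and 1.5 over the four periods (illustrative values).

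**Step 5: dropout.** Ordinary monotone dropout leaves the ranks unchanged. The SAP's carry-forward of dropout scores to the lower settings keeps the same pairing.

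**Step 6: early exits recorded as the Final Study Visit.** The exit counts here are assumed. Suppose one subject leaves after each of 80, 60 and 40%, and that last record is labelled visit 4. Rows: 37 × 4 + 1 + 2 + 3 = 154.
- Main effects become full rank: 7/7, 5/5, 5/5 and 3/3.
- With both as factors, the interaction still adds 0 df (16 columns, rank 7).
- With both linear, the correlation is −0.965 and the variance inflation factor (VIF) is 1/(1 − 0.9647²) = 14.4. It is 7.3 with 6 exits (148 rows) and 3.7 with 12 (136 rows), spread evenly over the three levels. These VIFs use the fixed-effect columns only and ignore the random subject effect.
- Removing the 3 exit records (151 rows), or labelling them by period (154 rows), returns the ranks to 7/4, 5/4, 5/4 and 3/2.

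All of the separation comes from 3 of 154 records.

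**Step 7: amplitude alone.** As a factor it has 4 columns and rank 4, on the planned schedule and in the three-exit case.

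**The case against.** The strongest reply is about consequence. The model is optional, SAP 7.9.2.1 rules out hypothesis testing for this objective, and the study is a descriptive feasibility study. The primary summary and the secondary means, changes and minimum amplitudes do not use the model. This stands, and it limits the weight of the point. It does not make the specified model estimable.

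Second, the analysis is not lost altogether. With both terms as factors on the planned schedule, the four fitted means are the same whichever term is dropped. That is correct: what is lost is the visit-adjusted amplitude effect and a meaningful interaction test.

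Third, exact aliasing depends on how the variables are defined. Settings are read from the device at each visit, and visit dates may vary by 3 days either way. Realised percentages or elapsed days would replace exact aliasing with near-collinearity. That softens the algebra but leaves the practical problem.

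Fourth, Protocol 9.10 does not say that an early-exit diary score enters this model or carries the Final Study Visit label. SAP 7.9.2.2 refers to scheduled visits, and Protocol Table 2 ties the final diary to 20%. This is fair. Step 6 is an illustration of the one documented route off the planned pairing, and the conclusion for the planned schedule does not need it.

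Finally, the confounding comes from the fixed descending order and no model removes it. This is also true, and it is a reason for the SAP not to include terms that imply otherwise.

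**Conclusion.** The concern holds. On the planned schedule, under the nominal reading of percent amplitude and visit, separate amplitude and visit effects are not identifiable. Amplitude given visit has 0 df in three of four codings; in the fourth it has 2 df, for non-linearity only. The interaction has 0 df in three codings; in the fourth it has 1 df, which is a quadratic in amplitude. If early-exit records break the alias, the separation rests on a few subjects whose leaving may itself be related to pain.

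This should be fixed, although the stakes are modest: no descriptive summary or decision rule for the primary or secondary objective depends on the model. Nothing is claimed about redacted text.

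**What to change.** In SAP 7.9.2.3:
- Remove visit and the amplitude-by-visit interaction from the fixed effects, along with the rule for keeping or dropping the interaction. Visit may stay as the within-subject ordering index for the covariance.
- Fit percent amplitude alone as the fixed effect, with subject as the random effect.
- Analyse each record, including any early-exit record, under the setting actually in use.
- State in the SAP and the report that the estimate combines lower amplitude with elapsed time and order, and that this design cannot separate them.

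The cost is a few sentences of SAP wording. Data collection and the descriptive summaries do not change. The edit does not remove the confounding; it makes explicit a limit that the design already has.

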7.9.2.4. Determination of Subject for Analysis

Subjects who proceed beyond the baseline visit and receive at least one programmed amplitude setting (treated analysis set).

7.9.3. Additional Objectives

[Redacted content]

7.10. Safety Evaluation

The safety objective is to characterize therapy and device related adverse events and device deficiencies.

Adverse events and device deficiencies will be coded and summarized using the most recent version of Medical Dictionary for Regulatory Affairs (MedDRA).

The adverse events will also be categorized by relationship to study device and/or therapy. Adverse events will be presented in summary tables displaying the number of serious events, the number of events, and the number and percentage of subjects with one or more events. A summary of all device or therapy related adverse events and of any deaths will also be provided. A detailed narrative of each serious device or therapy related adverse event will be provided.

Device deficiencies will be presented in summary tables displaying the number of deficiencies, and the number and percentage of subjects with deficiencies.

8. Validation Requirements

Statistical programming code that affects the result of the main analysis for the primary objective shall be validated using Level I validation, which is defined as the peer reviewer independently programs output and then compares the output with that generated by the original Statistical Programmer.

Statistical programming code that affects the result of the main analysis for the secondary object shall be validated using Level II validation, which is defined as the peer reviewer reviews the code; where appropriate, performs manual calculations or simple programming checks to verify the output.

In addition, the main statistical analyses that are planned for publication and have not been previously validated should be validated with at least Level II validation.

9. References

i. Hakkinen A, Kautiainen H, Jarvenpaa S, Arkela-Kautiainen M, Ylinen J. Changes in the total Oswestry Index and its ten items in females and males pre- and post-surgery for lumbar disc herniation: a 1-year follow-up. *Eur Spine J.* Mar 2007;16(3):347-352.

ii. Fairbank JC, Pynsent PB. The Oswestry Disability Index. *Spine (Phila Pa 1976).* Nov 15 2000; 25(22):2940-2952; discussion 2952.

iii. The EuroQol Group (1990). EuroQol-a new facility for the measurement of health-related quality of life. *Health Policy* 16(3):199-208.
